11.2 Analysis Plans

Phase I:

Toxicity type and severity by dose level will be summarized using frequency tables.

Phase II:

The analysis for phase II will include the patients who are treated at the MTD in phase I.

Toxicity type and severity will be summarized for each patient cohort using frequency tables.

Summary statistics will be provided for continuous variables. Frequency tables will be used to summarize categorical variables. The overall response rate for each patient cohort will be calculated and the Clopper Pearson confidence interval will be provided. Chi square test or Fisher's exact test will be used to evaluate the association between patient prognostic factor and response. The distribution of time-to-event endpoints including overall survival and progression free survival will be estimated using the method of Kaplan and Meier.

Comparison of time-to-event endpoints by important subgroups will be made using the log-rank test.

For the toxicity endpoint, per-treated analysis will be performed to include any patient who received the treatment regardless of the eligibility nor the duration or dose of the treatment received. For the efficacy endpoints, intend-to-treat analysis will be applied to the eligible patients.

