2.2 OBJECTIVES

2.2.1 Primary Objectives

Part 1 (phase 1).

1. To determine the maximum tolerated dose of lenalidomide plus obinutuzumab in relapsed/refractory indolent lymphoma.

Part 2 (phase 2).

1. To evaluate the safety of lenalidomide in combination with obinutuzumab in patients with relapsed/refractory indolent lymphoma.
2. To determine the overall response rate (ORR) of the combination in patients with relapsed/refractory indolent lymphoma.

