11. STATISTICAL CONSIDERATIONS

This is a single-center, open label, phase I/II study in patients with refractory or relapsed indolent lymphoma. The feasibility of administrating lenalidomide in combination with obinutuzumab and the MTD of the combination will be determined in the phase I part of the study. When the MTD has been established, the efficacy of the combination will be further evaluated in the phase II part of the study in two patient cohorts simultaneously. The two patient cohorts are the patients with follicular lymphoma (grade 1-3a) and the patients with either follicular lymphoma, marginal zone lymphoma, or SLL. A maximum of 72 patients (18 in phase I and 60 in phase II (30 patients each cohort); the patients treated at the MTD in phase I will be counted as the first group of patients treated in phase II) will be enrolled in this study on an intent-to-treat basis.

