11.1.2 Phase II

The primary objective for the phase II part is to further evaluate the safety and efficacy of lenalidomide when given in combination with obinutuzumab at the MTD of lenalidomide determined in phase I. The maximum number of patients that will be recruited for the phase II part is 60 (include additional 54 and the 6 patients treated at the MTD in phase I) with 30 for each of the two patient cohorts: the patients with follicular lymphoma (grade 1-3a) and the patients with either follicular lymphoma, marginal zone lymphoma or SLL. The patients who are treated at the MTD in the phase I part will be included in phase II (in relevant cohort). The objective response (complete response + partial response) after 6 cycles and DLT after 1 cycle will be monitored simultaneously using the Bayesian approach of Thall, Simon, Estey (1995, 1996) as extended by Thall and Sung (1998).

Cohort A: Patients with Follicular lymphoma

Historical data on 43 patients (Witzig, 2009) with relapsed or refractory indolent non-Hodgkin's lymphoma treated with lenalidomide show an objective response (OR) rate of 23% and DLT rate of under 30%. Independence was assumed between OR and DLT. It is expected for the current trial that the two-drug combination will improve the OR rate by 20% to 43% while the DLT rate is maintained at or below 30%. A sample size of 30 patients ensures that, if the trial is not terminated early, a posterior 90% credible interval for OR rate will have width of 0.283 at most, under the assumption of a 43% of OR rate. We will claim that the regimen is worth of further investigation if the lower limit of the posterior 90% credible interval for OR rate is higher than 0.23. The probabilities of OR and DLT for the historical data are modeled by beta distributions (*Beta* (9.89, 33.11) and *Beta* (12.9, 30.1), respectively). The prior probabilities of OR and DLT for the experimental regimen are also modeled by beta distributions (*Beta* (0.46, 1.54) and *Beta* (0.6, 1.4), respectively), which have the same *means* as the corresponding beta distributions for the historical data.

Denoting the historical probabilities of objective response rate and DLT rate by $\{p(\text{OR}, \text{H}), p(\text{DLT}, \text{H})\}$, the following decision criteria will be applied:

- 1) Let E correspond to the experimental treatment, stop if

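### Efficacy is analysed only in eligible patients, with no requirement that eligibility be judged blind to response; one exclusion can change the Cohort A claim, but only at exactly 11 responders

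*Combined protocol and SAP*

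**What the plan says.** Overall response rate is a primary phase II objective (2.2.1): "To determine the overall response rate (ORR) of the combination in patients with relapsed/refractory indolent lymphoma". Section 11 states that patients "will be enrolled in this study on an intent-to-treat basis", and 2.3.1 says the same; neither limits this to eligible patients.

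Section 11.2 then sets two analysis populations. Toxicity will "include any patient who received the treatment regardless of the eligibility nor the duration or dose of the treatment received". The next sentence reads "For the efficacy endpoints, intend-to-treat analysis will be applied to the eligible patients".

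The claim rule stands apart, in 11.1.2. In Cohort A the regimen is judged worth pursuing "if the lower limit of the posterior 90% credible interval for OR rate is higher than 0.23"; Cohort B uses the same rule with 0.30. The interval widths that justify the design are stated for 30 patients per cohort: "A sample size of 30 patients ensures that, if the trial is not terminated early".

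The plan does not say who decides eligibility after enrolment, when, or whether that person is unaware of response. It does not say whether an ineligible phase II patient is replaced, and it plans no efficacy analysis in all treated patients.

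**The concern.** A treated patient later found ineligible counts for safety but not for response. If that finding is made after the response is known, it can be related to the outcome, and the trial is open-label and single-centre. Several entry criteria in 3.1 and 3.2 involve judgement: whether a cytopenia or an abnormal laboratory value is due to the lymphoma, whether a concomitant disease is significant and uncontrolled, and whether transformation is under way. The last of these is plausibly linked to poor response.

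At stake are the primary response rate and the claim built on it. With 30 patients the claim depends on a whole-number threshold, so one or two exclusions can matter when the count falls next to it. The efficacy and safety denominators may also differ.

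**Working it through.** **Inputs** (11.1.2). Cohort A: prior Beta(0.46, 1.54), n = 30, claim if the lower limit exceeds 0.23, futility stops at 1 or fewer of 10 and 4 or fewer of 20. Cohort B: prior Beta(0.6, 1.4), n = 30, limit 0.30, stops at 2 or fewer of 10 and 6 or fewer of 20. The number of ineligible patients is not given; one of 30 (3.3%) and two of 30 (6.7%) are illustrations.

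**Formula.** With x responders among n patients and prior Beta(a, b), the posterior is Beta(a + x, b + n − x). The lower 90% limit is its 5th percentile.

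**The plan's own figures reproduce.** Cohort A at 43% of 30 (x = 12.9) has width 0.283, and Cohort B at x = 15 has width 0.287, both as stated. Exact binomial calculation with looks at 10 and 20 gives early-stopping probabilities of 0.5420 (Cohort A, true 23%) and 0.6491 (Cohort B, true 30%), matching the table rows for a DLT rate of 0.10.

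**Lower limits near the threshold**

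| Cohort | x/n | Lower limit | Claim? |
|---|---|---|---|
| A | 12/30 | 0.254 | yes |
| A | 11/30 | 0.226 | no |
| A | 11/29 | 0.234 | yes |
| A | 10/27 | 0.222 | no |
| A | 10/26 | 0.231 | yes |
| B | 14/30 | 0.315 | yes |
| B | 13/30 | 0.286 | no |
| B | 13/29 | 0.296 | no |
| B | 13/28 | 0.308 | yes |

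In Cohort A, one excluded non-responder changes the outcome only at x = 11; at x = 10 it takes four. In Cohort B, one is not enough at x = 13 and two are. In the other direction, dropping a responder from 12/30 gives 11/29, which lowers the estimate from 40.0% to 37.9% but still passes.

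**Probability of exactly 11/30 in Cohort A**, with futility stops: 3.5% at a true rate of 23%, 13.1% at 33%, 11.1% at 43%.

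**Claim probability when the true rate equals the historical rate.** Sum the binomial probabilities over paths that pass both looks and end at or above the threshold. Toxicity stops are ignored. Removals are taken from patients after the second look, so the early stops are unchanged.

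| Scenario | A, true 23%, one removed | B, true 30%, two removed |
|---|---|---|
| All 30 kept (A: 12 or more; B: 14 or more) | 2.7% | 3.8% |
| Removal regardless of response (A: 11 or more of 29; B: 13 or more of 28) | 5.0% | 4.7% |
| Non-responders always removed (A: 11 or more of 30; B: 13 or more of 30) | 6.2% | 7.8% |

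In Cohort A, 2.22 of the 3.47 points of worst-case rise (4.97 − 2.75 against 6.21 − 2.75, from unrounded values) come from the threshold falling to 11 at n = 29, without any selection on response. That is about two thirds. In Cohort B the share is 0.89 of 3.98 points, about a fifth.

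**The other interval.** Section 11.2 also plans a Clopper-Pearson interval, with no stated level. Its lower limits at 11/30 and 11/29 are 0.221 and 0.229 at 90%, and 0.199 and 0.207 at 95%. All are below 0.23, so the change of outcome arises only under the Bayesian rule.

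**The case against.** A reader might infer that the plan flatly contradicts itself. That goes too far. Sections 2.3.1 and 11 speak of enrolment; only 11.2 defines analysis sets, and it names both openly. Intent-to-treat among eligible patients still keeps those who stop early or do not comply. What stands is that the label promises more than the set delivers, and that the toxicity set ignores eligibility while the efficacy set does not.

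A reader might also infer that eligibility will be re-judged once responses are in. No section says so. The criteria are pre-treatment, and many are laboratory thresholds. The documents do not rule re-judgement out either, so it is an open route to bias and not a described practice. Exclusions can also remove responders.

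The claim rule sits in 11.1.2 and is framed on 30 patients. Applying the 11.2 set to it is reasonable, because response is an efficacy endpoint, but the plan does not say so. If ineligible patients were replaced, n would stay at 30 and the change of threshold would not arise.

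Finally, the 6.2% and 7.8% figures assume that non-responders are always available to remove and always removed. They are upper bounds for those numbers of removals, not expected effects.

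**Conclusion.** The point holds as a correctable weakness in the primary efficacy analysis. The efficacy set is restricted after enrolment by a judgement that the plan does not require to be made blind to response, and the resulting bias in the response rate could go either way.

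The effect on the claim is limited. In Cohort A a single exclusion matters at one count only, and the claim probability at a true 23% goes from 2.7% to 5.0% without selection or 6.2% at worst. In Cohort B two exclusions are needed, and 3.8% becomes 4.7% or 7.8%. These figures assume that the 11.2 set feeds the 11.1.2 rule, that excluded patients are not replaced, and that one or two patients are excluded.

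The documents do not support reading this as an inflated false-positive rate already built into the design. How to count patients without a six-cycle response assessment is a separate question that this sentence does not settle.

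**What to change.** In 11.2, define the primary efficacy set as all phase II patients who received study drug, including the phase I patients treated at the MTD. This is the set already used for phase II toxicity. State that it is also the denominator for the claim rule in 11.1.2. Define it by cohort membership and receipt of drug, not by starting dose, because 5.2.1 caps the first-cycle lenalidomide dose for SLL patients. Report the eligible-only result as a sensitivity analysis, with eligibility judged from baseline data by someone unaware of response.

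The cost is a sentence or two of text, with no added patients or visits. The reported response rate may be slightly lower. Patients enrolled but never treated are still left out, so the set should be called all-treated and not intent-to-treat.

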12. REPORTING OF ADVERSE EVENTS

12.1 ASSESSMENT OF SAFETY

Safety assessments will consist of monitoring and reporting adverse events (AEs) and serious adverse events (SAEs) per protocol. This includes all events of death, and any study specific issue of concern.

12.1.1 ADVERSE EVENTS

An AE is any unfavorable and unintended sign, symptom, or disease temporally associated with the use of an investigational medicinal product (IMP) or other protocol-imposed intervention, regardless of attribution.

This includes the following:AEs not previously observed in the subject that emerge during the protocol-specified AE reporting period, including signs or symptoms associated with non-Hodgkin's lymphoma that were not present prior to the AE reporting period.

Complications that occur as a result of protocol-mandated interventions (e.g., invasive procedures such as cardiac catheterizations).

- If applicable, AEs that occur prior to assignment of study treatment associated with medication washout, no treatment run-in, or other protocol-mandated intervention.
- Preexisting medical conditions (other than the condition being studied) judged by the investigator to have worsened in severity or frequency or changed in character during the protocol-specified AE reporting period.

12.1.2 SERIOUS ADVERSE EVENTS

Serious Adverse Event (SAE) Reporting Requirements for M D Anderson Sponsor Single Site IND Protocols

An adverse event or suspected adverse reaction is considered "serious" if, in the view of either the investigator or the sponsor, it results in any of the following outcomes:

- Death
- A life-threatening adverse event
- Inpatient hospitalization or prolongation of existing hospitalization
- A persistent or significant incapacity or substantial disruption of the ability to conduct normal life functions.
- A congenital anomaly/birth defect.

Important medical events that may not result in death, be life-threatening, or require

hospitalization may be considered a serious adverse drug experience when, based upon appropriate medical judgment, they may jeopardize the patient or subject and may require medical or surgical intervention to prevent one of the outcomes listed in this definition. Examples of such medical events include allergic bronchospasm requiring intensive treatment in an emergency room or at home, blood dyscrasias or convulsions that do not result in inpatient hospitalization, or the development of drug dependency or drug abuse (21 CFR 312.32).

- Important medical events as defined above, may also be considered serious adverse events. Any important medical event can and should be reported as an SAE if deemed appropriate by the Principal Investigator or the IND Sponsor, IND Office.
- All events occurring during the conduct of a protocol and meeting the definition of a SAE must be reported to the IRB in accordance with the timeframes and procedures outlined in "The University of Texas M. D. Anderson Cancer Center Institutional Review Board Policy on Reporting Adverse Events for Drugs and Devices".
- Serious adverse events will be captured from the time of the first protocol-specific intervention, until 30 days after the last dose of drug, unless the participant withdraws consent.
- Serious adverse events must be followed until clinical recovery is complete and laboratory tests have returned to baseline, progression of the event has stabilized, or there has been acceptable resolution of the event.
- All SAEs, expected or unexpected/ initial or follow up, must be reported to the IND Office within 5 working days of knowledge of the event regardless of the attribution.
- Death or life-threatening events that are unexpected, possibly, probably or definitely related to drug must be reported (initial or follow up) to the IND Office within 24 hours of knowledge of the event
- Additionally, any serious adverse events that occur after the 30 day timeline that are related to the study treatment must be reported to the IND Office. This may include the development of a secondary malignancy.
- The electronic SAE application (eSAE) will be utilized for safety reporting to the IND Office and MD Anderson IRB.
- All events reported to the supporting company must also be reported to the IND Office

Reporting to FDA:

- Serious adverse events will be forwarded to FDA by the IND Sponsor according to 21 CFR 312.32.

It is the responsibility of the PI and the research team to ensure serious adverse events are reported according to the Code of Federal Regulations, Good Clinical Practices, the protocol guidelines, the sponsor's guidelines, and Institutional Review Board policy.

12.2 METHODS AND TIMING FOR ASSESSING AND RECORDING SAFETY VARIABLES

The investigator is responsible for ensuring that all AEs and SAEs that are observed or reported during the study, are collected and reported to the FDA, appropriate IRB(s), and Genentech, Inc. in accordance with CFR 312.32 (IND Safety Reports).

12.2.1 ADVERSE EVENT REPORTING PERIOD

The study period during which all AEs and SAEs must be reported begins after the first protocol intervention, and ends 30 days following the last administration of study treatment or study discontinuation/termination, whichever is earlier. After this period, investigators should only report SAEs that are attributed to prior study treatment.

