Patients that do not have at least a partial remission following 12 cycles of combination therapy will not continue with extended obinutuzumab treatment.

TREATMENT REGIMEN

*(GA101 will be given in divided doses on first dose in cycle 1; 100mg IV on day 1, and 900mgIV on day 2, subsequent doses will be given over 1 day)

This research study protocol allows the subject to receive up to 21 infusions of obinutuzumab. Even if the treatment is shown to be of benefit, additional infusions of obinutuzumab beyond that allowed in the protocol cannot be given to the subject while they are participating in this study.

Visit schedule and assessments

Screening Assessments and all on study scheduled visits and assessments are outlined in Table of Study Assessments. All timepoints outlined in the Schedule of Assessments allow variation of +/- 3 days.

Due to the drug delivery from an outside facility, clinicians should allow up to 72 hours from patient assessment/evaluation to the start of each cycle.

Pregnancy testing and counseling must be performed if a subject misses her period or if her pregnancy test or her menstrual bleeding is abnormal. Study drug treatment must be discontinued during this evaluation. In addition to the required pregnancy testing, the Investigator must confirm with FCBP that she is continuing to use two reliable methods of birth control at each visit.

An unscheduled visit can occur at any time during the study. Source must be maintained for these unscheduled visits. The date for the visit and any data generated must be recorded on the appropriate CRF. Source documents for these unscheduled visits must also be maintained.

At treatment discontinuation, subjects will undergo off study evaluations per the Schedule of Assessments, Section 2. In addition, a safety assessment will be done approximately 28 days post the last dose of study drug.

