should be referred to an obstetrician-gynecologist, preferably one experienced in reproductive toxicity for further evaluation and counseling.

The Investigator will follow the female subject until completion of the pregnancy, and must notify Celgene Drug Safety immediately about the outcome of the pregnancy (either normal or abnormal outcome) using the Pregnancy Follow-up Report Form. If the outcome of the pregnancy was abnormal (e.g., spontaneous or therapeutic abortion), the Investigator should report the abnormal outcome as an AE. If the abnormal outcome meets any of the serious criteria, it must be reported as an SAE to Celgene Drug Safety immediately by facsimile, or other appropriate method, within 24 hours of the Investigator's knowledge of the event using the SAE Report Form.

All neonatal deaths that occur within 28 days of birth should be reported, without regard to causality, as SAEs. In addition, any infant death after 28 days that the Investigator suspects is related to the in utero exposure to the IP should also be reported to Celgene Drug Safety immediately by facsimile, or other appropriate method, within 24 hours of the Investigator's knowledge of the event using the SAE Report Form.

Male Subjects

If a female partner of a male subject taking investigational product becomes pregnant, the male subject taking lenalidomide should notify the Investigator, and the pregnant female partner should be advised to call their healthcare provider immediately.

Celgene Drug Safety Contact Information:

Celgene Corporation
Global Drug Safety and Risk Management
[name]
[name]
[name]
[contact]
E-mail: [contact]

Post-Study Adverse Events

The investigator should expeditiously report any SAE occurring after a subject has completed or discontinued study participation if attributed to prior obinutuzumab or lenalidomide exposure. If the investigator should become aware of the development of cancer or a congenital anomaly in a subsequently conceived offspring of a female subject, including pregnancy occurring in the partner of a male study subject who participated in the study, this should be reported as an SAE adequately to Genentech drug Safety during follow up period

Reconciliation

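### Section 12.2.1 can be read as ending AE and SAE reporting at study exit, short of the 30 days after the last dose that Section 12.1.2 sets for SAEs

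*Combined protocol and SAP*

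**What the plan says.** **Reporting period.** Section 12.2.1 covers all AEs and SAEs. The period opens after the first protocol intervention and "ends 30 days following the last administration of study treatment or study discontinuation/termination, whichever is earlier". It adds: "After this period, investigators should only report SAEs that are attributed to prior study treatment".

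**SAE capture.** Section 12.1.2 gives SAEs their own window, which runs "until 30 days after the last dose of drug, unless the participant withdraws consent". Every SAE, expected or not, "must be reported to the IND Office within 5 working days of knowledge of the event regardless of the attribution". Beyond that window, "any serious adverse events that occur after the 30 day timeline that are related to the study treatment must be reported" to the IND Office. The post-study paragraph in Section 12.3.2 says much the same: "The investigator should expeditiously report any SAE occurring after a subject has completed or discontinued study participation if attributed to prior obinutuzumab or lenalidomide exposure".

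**Deaths.** The death rule in Section 12.3.2 requires deaths to be reported regardless of attribution, but only within the reporting period of Section 12.2.1, which it cites.

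**Leaving treatment and leaving the study.** Section 6.4 follows patients who stop treatment for at least 6 months. Section 4.3 states that "a safety assessment will be done approximately 28 days post the last dose of study drug", and Sections 6.4 and 9.3 repeat this. Section 7.1 takes patients off the study, not only off drug, for active HBV infection or hepatitis and for severe or life-threatening anaphylaxis or hypersensitivity. Section 9.3 ends protocol follow-up when another lymphoma treatment starts; Section 6.4 keeps survival follow-up in that case.

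**The concern.** Two sections give the same staff different end dates for mandatory safety reporting, and the death rule takes its period from the one that may be shorter. If the earlier-of clause in 12.2.1 closes the window at study exit, a patient taken off study soon after a dose drops out of routine AE reporting while 12.1.2 still requires SAE capture.

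This matters because safety is a primary phase II objective (Section 2.2.1), and Section 11.2 tabulates toxicity type and severity by cohort, including every patient who received treatment. Non-serious AEs are the most exposed, since no section other than 12.2.1 sets a reporting window for them after the last dose.

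**Working it through.** The plan states no figure on this point, so the check compares the sections and adds simple window arithmetic.

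**Input.** Let *d* be the number of days from last dose to study discontinuation. The documents give no distribution of *d*, so the values below are illustrative.

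**Reading A: the period ends at the earlier of (last dose + 30 days) and study discontinuation.** The shortfall against 12.1.2 is max(0, 30 − *d*).

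| *d* (days) | Shortfall (days) |
|---|---|
| 0 | 30 − 0 = 30 |
| 7 | 30 − 7 = 23 |
| 14 | 30 − 14 = 16 |
| 28 | 30 − 28 = 2 |
| 30 or more | 0 |

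The maximum is 30 days.

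**Reading B: the 30 days run from the earlier of last dose and study discontinuation.** A treated patient's last dose cannot come after study discontinuation. The period therefore always ends at last dose + 30 days, the shortfall is 0 for every *d*, and 12.2.1 agrees with 12.1.2.

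**Who is exposed on reading A.**
- Patients discontinued from the study under 7.1 within 30 days of the last dose.
- Arguably, patients who start next-line therapy within 30 days, because 9.3 ends protocol follow-up then.
- Not patients who withdraw consent: 12.1.2 makes the same exception, and 6.4 stops their follow-up at that date.
- Not patients who only stop treatment: they stay in follow-up under 6.4. A site could blur this, because Section 8 is headed as criteria for study discontinuation but lists reasons to stop study drug, and Section 4.3 calls for off-study evaluations at treatment discontinuation.

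**What is exposed for those patients on reading A.**

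| Event after exit, up to day 30 | 12.2.1 | 12.1.2 and other sections | Result |
|---|---|---|---|
| Non-serious AE | Not reported | No window set | No reporting requirement |
| SAE not attributed to treatment | Not reported | 12.1.2: report | Conflicting instructions |
| Death not attributed to treatment | Not reported (12.3.2 inherits this period) | 12.1.2: death is an SAE, report | Conflicting instructions |
| SAE attributed to treatment | Report | 12.1.2 and 12.3.2: report | Covered |

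The safety assessment at about day 28 would fall outside the reporting period for these patients only. For everyone still on study, day 28 lies inside the 30 days on either reading.

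**The case against.** The strongest reply is that 12.2.1 is ambiguous, not wrong. Reading B is grammatical and removes the conflict entirely.

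A reader might answer that reading B leaves the earlier-of clause with nothing to do, so reading A must be intended. The documents do not support that step. The period opens after the first protocol intervention, and Section 12.1.1 counts AEs arising before study treatment is assigned. A patient who has a protocol procedure and leaves undosed has no last administration, so the discontinuation limb is what closes the period. The clause has work to do on reading B, and reading A is natural but not forced.

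A reader might also infer that early leavers lose a month of safety data. That is too broad. Section 12.1.2 independently requires all SAEs to day 30, attributed SAEs remain reportable without an end date, and Section 13 requires any SAE to reach the lenalidomide supplier within 24 hours. Unattributed SAEs go missing only if staff follow 12.2.1 and set 12.1.2 aside.

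A third inference is that the truncation is informative and understates toxicity. Exits under 7.1 are indeed toxicity-related, but Section 6.4 counts patients whose drug is interrupted for toxicity among those who remain on study. No exit rate or timing is given from which a bias could be sized.

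Nor is an effect on the toxicity stopping rule shown. DLT is defined and assessed over the first 28-day course under Section 11.1.1, separately from 12.2.1.

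These replies narrow the point but do not remove it. The two sections differ on a natural reading, the death rule inherits the difference, and non-serious AEs have no second rule to fall back on.

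**Conclusion.** The point holds as a conflict on one natural reading of Section 12.2.1. For a treated patient who actually leaves the study within 30 days of the last dose, other than by withdrawing consent, the reporting period is shorter than the SAE window of 12.1.2 by 30 − *d* days, at most 30. Within that gap non-serious AEs have no reporting requirement, and unattributed SAEs and deaths are under conflicting instructions.

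This rests on reading A; on reading B the gap is zero. It also takes study discontinuation to mean leaving the study. A site that equated it with stopping drug would widen the affected group.

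The number of patients affected cannot be derived from the documents. Sample size, stopping boundaries and operating characteristics do not depend on the point. It is a modest reporting defect, worth correcting because it bears on AE capture for a primary objective and costs almost nothing to remove.

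**What to change.** Reword the end of the period in Section 12.2.1. For patients who received any study treatment, AE and SAE reporting ends 30 days after the last dose of either study drug, unless consent is withdrawn, as in 12.1.2. For patients who never received a dose, it ends at study discontinuation.

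The death rule in 12.3.2 then takes the corrected period through its existing cross-reference and needs no edit. For treated patients, the period also stops depending on how a site interprets study discontinuation.

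The cost is one sentence. The safety assessment at about day 28 stays where it is, and no visit is added. The extra work is at most 30 days of AE recording for each patient who leaves the study early.
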